1.1.5. Results: adherence rates

Actual behaviour: reducing/rescheduling outdoor activities

In the studies investigating actual adherence to the health advice to avoid, reduce or reschedule outdoor activities during poor air quality, overall adherence rates ranged from 9.7% (12) to 70.7% (27), with median adherence rates of 36% (11).

Actual behaviour: additional protective behaviours

In the studies investigating a wider range of actual protective behaviours, going beyond the decision to simply reduce or reschedule outdoor activities, overall adherence (including also behaviours performed less than monthly during moderate or high pollution episodes) ranged from 17.7% (26) to 98.1% (13), with median adherence rates of 42% (18). The most common responses reported by all study participants included: avoiding busy or polluted road (with adherence rates ranging from about 10% to 52.5% (17,18,21), spending more time indoors (ranging from about 30% to 58.7% (13,18,21), adjusting or rescheduling travels or other outdoor activities (41.4%), changing means of travel (38.6%)(21), and avoiding strenuous exercise or other outdoor activities (ranging from 17.4% to 88.4% (13,17,18,22,26). Other behaviours included taking a reliever medication (ranging between 30.5% and 50% (17,18), taking a preventative medication (30.5%-38.5% (17)), getting advice from GP (about 1% (18,26)), and wearing a mask (6.4% to 8.1% (13,26)).

Intended behaviour

These studies showed an overall intention to adhere ranging from 36.4% (20) to about 81.8% (27) (the latter refers to a group of respondents with severe lung disease).

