4 RESEARCH QUESTION/AIM(S)

The purpose of the present study is to test whether theory and evidence-based alternative communication formats, targeting message specificity and previously identified psychosocial predictors of adherence, could improve the behavioural impact of existing alert systems, compared to the official messages sent in association with the UK AQIs.

Research questions

Primary questions:

1) What is the main effect of using behaviourally enhanced messages, compared to the currently used DAQI messages, to present the health advice associated with air quality notifications for a hypothetical high air pollution scenario on adherence intentions?

Prediction:

A) The behaviourally enhanced messages will lead to stronger intentions to adhere to recommendations.

2) What is the main effect of using a behaviourally enhanced message, compared to the currently used DAQI messages, to present the health advice associated with air quality notifications on actual behaviour changes at four weeks?

Prediction:

A) The enhanced messages will lead to greater behaviour changes.

3) In case of a real alert being issued during the study period, how do the different messages affect actual behaviour change?

Prediction:

A) The enhanced messages will lead to greater behaviour change.

Secondary questions:

4) If there is a format effect, which variables mediate the relationship between the information format and behaviour change?

5) Which factors are associated with greater behaviour change across all groups?

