Moderate 4-6	Enjoy your activities as usual ^a	Adults and children with lung problems, and adults with heart problems, who experience symptoms, should consider reducing strenuous physical activity, particularly outdoors. ^b	
Enjoy your activities as usual. However, if you wanted you, you can reduce your exposure to pollution by reducing levels and length of physical activity outdoors.
 
You can also consider changing:
 
 • Travel route or • Exercise location (e.g. use our app to find less polluted roads or parks) or • Time (e.g. mornings or less polluted times). ^e 	
Adults and children with lung problems, adults with heart problems, and older people, should reduce levels and length of physical activity outdoors.
 
Where possible, change:
 
 • Travel route or • Exercise location (e.g. use our app to find less polluted roads or parks) or • Time (e.g. mornings or less polluted times). ^h
High 7-9	Anyone experiencing discomfort such as sore eyes, cough or sore throat should consider reducing activity, particularly outdoors. ^c	Adults and children with lung problems, and adults with heart problems, should reduce strenuous physical exertion, particularly outdoors, and particularly if they experience symptoms. People with asthma may find they need to use their reliever inhaler more often. Older people should also reduce physical exertion. ^d	
Anyone who experiences sore eyes, cough or sore throat should consider limiting their exposure to air pollutants.
 
To do this, you don't need to stay indoors, instead you can reduce levels and length of physical activity outdoors.
 
You can also consider changing:
 
 • Travel route or • Exercise location (e.g. use our app to find less polluted roads or parks) or 	
Adults and children with lung problems, adults with heart problems, and older people, should reduce levels and length of physical activity outdoors.
 
People with asthma may find they need to use their reliever inhaler more often.
 
Where possible, change:
 
 • Travel route or • Exercise location (e.g. use our app to find less polluted roads or parks) or

SHORT TITLE/ACRONYM: Improving the health impact of air quality alerts v.3

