5.6 MEASURES

Table 4. Summary of measures.

Timing	Measure	How it will be measured
First Online Questionnaire – After reading hypothetical high air pollution scenario	Baseline intentions ^a to adopt protective behaviours in response to hypothetical, high air pollution alert	Assuming the situation described was happening right now, how much would you agree with the following statements? 
 - I intend to follow the recommendations received with the air alert to reduce exposure to air pollution - I will avoid going outdoors - I intend to reduce length or level of my physical activity outdoors - I intend to change my travel route - I intend to change my exercise location - I intend to change the time when I travel - I intend to change the time when I exercise outdoors
	Baseline medication adherence intentions ^a	If you have lung problems: 
 - I intend to use my preventer inhaler daily - I intend to carry my reliever inhaler with me
	Other baseline intention ^a (not advised behaviours)	
 - I will wear a mask as a protection from air pollution - I intend to reduce length or level of my physical exercise indoors
	Previous protective behaviour ^b	- In the past 4 weeks, how often have you taken action to reduce exposure to air pollution, I response to hearing or reading an air quality forecast?
	Planning	
 - In the last 4 weeks, to reduce your exposure to air pollution, have you considered making permanent changes to your daily travel route or exercise place and time?^c - In the last 4 weeks, how often have you checked air quality information before doing physical activity outdoors?^b
	Physical activity ^d	- To stay healthy, the NHS recommends at least 150 minutes of moderate physical activity (e.g. cycling, fast walking, swimming) every week (e.g. 30 minutes 5 days a week). Based on this, how physically active were you in the last week?
	Symptoms ^c	- Have you ever experienced symptoms caused by air pollution?
Air Alert period – Online questionnaires	Alert recall ^e	- Recently we sent you an air quality alert about poor air quality. What was the level of air pollution reported?

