	Actual Behaviour change ^c	In response to receiving the air quality alert: 
 - I reduced length or level of my physical activity outdoors - I changed my travel route - I changed my exercise location - I changed the time when I travelled - I changed the time when I exercised outdoors - If you answered no, please report the reasons [text box].
	Medication adherence ^c	If you have lung problems: 
 - I used my preventer inhaler daily - I carried my reliever inhaler with me when going outdoors. - If you answered no, please report the reasons [text box].
Final Online Questionnaire – at 4 weeks	Behaviour change at 4 weeks ^b	- In the past 4 weeks, how often have you taken action to reduce exposure to air pollution, I response to hearing or reading an air quality forecast?
	Physical activity ^d	- To stay healthy, the NHS recommends at least 150 minutes of moderate physical activity (e.g. cycling, fast walking, swimming) every week (e.g. 30 minutes 5 days a week). Based on this, how physically active were you in the last week? ^e
	Action planning	
 - In the last 4 weeks, to reduce your exposure to air pollution, have you considered making permanent changes to your daily travel route or exercise place and time?^c - In the last 4 weeks, how often have you checked air quality information before doing physical activity outdoors?^b
	Worry ^a	Adapted from Witte et al. (34) 
 - The information received through the CityAir app made me worry about the possibility of suffering health effects from exposure to air pollution

	- The information received through the CityAir app made me nervous and tense about the possibility of suffering health effects from exposure to air pollution
Severity ^a	Adapted from Witte et al. (34)
	- Air pollution is a severe threat to my health
Conditional susceptibility ^f	- How likely do you think you are to suffer from health effects due to air pollution if you do not take any action to reduce exposure? - How likely do you think people of your same age and sex are to suffer from health effects due to air pollution if they do not take any action to reduce exposure?
Response efficacy ^a	Adapted from Witte et al. (34)
	- Following the health advice received through the CityAir app is effective in protecting me from exposure to air pollution

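### The alert-period questionnaire has no item on avoiding the outdoors, so a gain on the route, location or time items may partly be one action replacing another

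*Combined protocol and SAP*

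**What the plan says.** Section 4 lists the real-alert question among the primary questions: "In case of a real alert being issued during the study period, how do the different messages affect actual behaviour change". The prediction is: "The enhanced messages will lead to greater behaviour change".

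Table 4 in section 5.6 measures this with five items answered yes, no or not sure. They cover reduced outdoor activity ("I reduced length or level of my physical activity outdoors"), travel route, exercise location, travel time and exercise time ("I changed the time when I exercised outdoors"). There is also a free-text prompt, "If you answered no, please report the reasons [text box", and two inhaler items for people with lung problems.

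The first and the week-4 questionnaires both include the intention item "I will avoid going outdoors", listed separately from the item on reducing outdoor activity.

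Section 1.1.5 names among the most common protective responses "spending more time indoors (ranging from about 30% to 58.7" per cent. In Table 2 (section 5.5), the enhanced High message for the general public says "you don't need to stay indoors, instead you can reduce levels and length of physical activity outdoors", then offers changes of route, exercise location and time.

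Section 6.1 plans chi-square tests on the proportions reporting actual behaviour change, in relation to a real moderate episode. It does not say whether each item is tested alone or the five are combined.

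**The concern.** The intervention text points away from a response that the alert-period questionnaire does not record and towards responses that it does record. Suppose some people who would have stayed in under the usual message change their route under the enhanced one. The route item then rises in the enhanced arm although the share of people protecting themselves is the same. The prediction concerns more behaviour change, and part of the apparent support for it would be a change in the kind of action.

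The reverse also matters. If the enhanced message leads fewer people to stay in when it tells them they need not, that is a result worth reporting, and no alert-period item measures it directly. The information cannot be recovered once the alert has passed.

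**Working it through.** The plan states no figure on this point, so there is none to reproduce. The check sets the questionnaires side by side and then illustrates the possible size.

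**1. Coverage of avoiding the outdoors**

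| Place in the plan | Covered? |
|---|---|
| Baseline intentions (Table 4) | Yes, own item |
| Week-4 intentions (Table 4) | Yes, own item |
| Alert-period behaviour (Table 4) | No, 0 of 5 items |
| Review of common responses (1.1.5) | Yes, about 30% to 58.7% |
| Enhanced High message, general public (Table 2) | Yes, described as unnecessary |

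**2. How a person who stays in can answer**

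- *Ticks reduced outdoor activity.* If such a person would instead change route under the enhanced message, the route item rises and the reduced-activity item may fall. A combined any-of-five outcome does not move. The switch is partly visible, but a fall in the reduced-activity item could mean less staying in or less cutting back while outdoors.
- *Ticks none of the five.* The route item and any-of-five both rise although no more people acted.

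**3. Illustrative size**

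Inputs:
- Share staying indoors: 30% to 58.7% (section 1.1.5).
- Fraction who switch to a measured action: one third (assumed).
- Arm size: 240 / 1.2 = 200, and 200 / 2 = 100 (from the 20% inflation in section 5.3). This assumes that every retained participant receives an alert and answers.
- Starting proportion: 36% (assumed). In section 1.1.5 this is the median for reducing or rescheduling outdoor activity. For avoiding busy or polluted roads the section gives about 10% to 52.5%.
- Two-sided alpha 0.05.

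Spurious gap: 30 / 3 = 10 points; 58.7 / 3 = 19.6, about 20 points.

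Power = Φ[(d − 1.96 × se0) / se1], where se0 = √(p̄(1 − p̄) × 2/n) and se1 = √((p1(1 − p1) + p2(1 − p2))/n).

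- 36% v 56%: se0 = √(0.46 × 0.54 × 0.02) = 0.0705; se1 = √((0.2304 + 0.2464)/100) = 0.0691; (0.20 − 0.1381)/0.0691 = 0.896; power 0.81.
- 36% v 46%: se0 = √(0.41 × 0.59 × 0.02) = 0.0696; se1 = √((0.2304 + 0.2484)/100) = 0.0692; (0.10 − 0.1363)/0.0692 = −0.525; power 0.30.

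**4. Sensitivity**

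Here total action is the same in both arms (50%, 60% or 70%), and people who only stay in tick none of the five items.

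| Indoors only, control v enhanced | Spurious gap | Chance of a significant result |
|---|---|---|
| 30% v 10% | 20 points | 0.81 to 0.88 |
| 20% v 10% | 10 points | 0.29 to 0.32 |
| 10% v 5% | 5 points | about 0.11 |

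**The case against.** **The planned test is for a moderate episode.** The wording against staying in appears only in the High general-public message. No Moderate message mentions it, and at Moderate the usual general-public message advises carrying on as normal, so a large group of controls staying in is unlikely there. This stands and weakens the mechanism for the test described in section 6.1. It does not remove it, because the enhanced Moderate messages add route, location and time changes that the usual ones lack. The research question itself is not limited to moderate alerts.

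**Staying in will be recorded as reduced outdoor activity.** Often it will, and substitution is then partly visible. A reader might infer that question 3 cannot distinguish more action from substitution at all, or that the prediction would be accepted on the route item alone. The documents support neither: the five items can be read together, and section 6.1 names no deciding item. What remains is that the reduced-activity item merges two responses that the intention questionnaires keep apart.

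**Other items fill the gap.** The week-4 questionnaire repeats the intention, asks how often any action was taken, and asks about stopping exercise altogether. The free text asks for reasons for a no. These help, but none gives a proportion per alert and per arm.

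**The numbers are constructed.** The one-third switch is assumed. The review's indoor range is not shown to be a per-alert rate for London; its sources include a study of emergency communication in a wildfire. The power figures show what is possible and do not predict.

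**Masks and indoor exercise.** A reader might extend the point to these, since both are asked as intentions and not after an alert. The plan classes both as not advised, mask use in its review is 6.4% to 8.1%, and nothing in the messages suggests switching away from either.

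**Conclusion.** The point holds in a limited form. The omission is plain from Table 4, and it leaves a primary question unable to separate cleanly more people acting from one action replacing another. It also means that a fall in avoidance after a real alert cannot be measured directly.

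The mechanism is clearest for High alerts to the general public and weaker for the moderate episode in section 6.1. The size is unknown. With 100 per arm and assumed switching, a spurious gap of 20 points would be significant about 81% of the time, one of 10 points about 30%, and one of 5 points about 11%. A reader might take the first figure as the expected outcome. It rests on the top of the review's range, an assumed one-third switch and an assumed 36% starting proportion, so the documents do not support that reading.

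**What to change.** Add one item to the alert-period questionnaire, *I avoided going outdoors*, answered yes, no or not sure. It is the past-tense form of an intention item that the plan already uses.

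In section 6.1, compare this item between arms as an outcome in its own right. Report the share taking any protective action, counting this item, beside the results for the five advised actions. State in advance that a rise in the advised actions without a rise in the any-action share will be read as a change in the kind of action.

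Past-tense mask and indoor-exercise items are optional.

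The cost is one more item in a short questionnaire and one or two more comparisons, which should be labelled as supporting the main test so that they do not add to the number of primary tests.

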Targeted Variable	General population	At risk - other	At risk: lung-specific	At risk: heart-specific	At-risk: combo
Response efficacy	Taking a side street route cuts a person's exposure to air pollution by half	Taking a side street route cuts a person's exposure to air pollution by half	Taking a side street route cuts a person's exposure to air pollution by half	Taking a side street route cuts a person's exposure to air pollution by half	Taking a side street route cuts a person's exposure to air pollution by half
			If you have a preventer inhaler, using it every day will reduce the inflammation that causes asthma. Your reliever inhaler will help to ease symptoms straight away.		If you have a preventer inhaler, using it every day will reduce the inflammation that causes asthma. Your reliever inhaler will help to ease symptoms straight away.
Response costs (i.e. negative consequences associated with the recommended behaviour)	The CityAir App can help you find side street routes, which do not necessarily add to your total travel time, and may give you a more pleasant journey.	The CityAir App can help you find side street routes, which do not necessarily add to your total travel time, and may give you a more pleasant journey.	The CityAir App can help you find side street routes, which do not necessarily add to your total travel time, and may give you a more pleasant journey.	The CityAir App can help you find side street routes, which do not necessarily add to your total travel time, and may give you a more pleasant journey.	The CityAir App can help you find side street routes, which do not necessarily add to your total travel time, and may give you a more pleasant journey.

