Medication response efficacy ^a	If you have lung problems: - Taking my preventer medications daily is effective in helping me to control my asthma - Carrying my reliever medication with me is an effective way to protect my health
Self-efficacy ^a	Items adapted from Witte et al (34) and Rhode et al (35)
	- I am confident I would be able to follow the health advice received through the CityAir app, if I wanted to
Medication self-efficacy ^a	Items adapted from Witte et al (34) and Rhode et al (35)
	- If you have lung problems: I am confident I would be able to take my preventer inhaler every day , if I wanted to - I am confident I would be able to remember to carry my reliever inhaler with me during days of poor air quality, if I wanted to
Response costs ^a	- I do not have enough time to follow the health advice received through the CityAir app - Taking side roads makes my journey too long
Medication response costs ^a	If you have lung problems: - Using the preventer inhaler daily is not safe - Using the preventer inhaler daily makes me dependent on it
Unwanted consequences of intervention ^a	- In the last 4 weeks I stopped exercising altogether due to receiving alerts about poor air quality - In the last 4 weeks, I made an emergency /unplanned visit to A&E or visited my GP due to symptoms caused by air pollution
Sensory cue prevalence ^a	- I trust my own perception of air quality more than any official air quality alert
Credibility ^g	- Meyer's credibility index (36,37) (α=.67)
Clarity ^h	- Overall, how clear were the messages received?
Perceived informed choice ^a	- I received enough information to make an informed choice on how to reduce my exposure to air pollution
Intentions ^a to adopt protective behaviour in response to hypothetical, high air pollution alert	[After reading again the high air pollution hypothetical scenario and tailored advice] - I intend to follow the recommendations received with the air alert to reduce exposure to air pollution - I will avoid going outdoors - I intend to reduce length or level of my physical activity outdoors - I intend to change my travel route - I intend to change my exercise location - I intend to change the time when I travel - I intend to change the time when I exercise outdoors

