Medication adherence intentions ^a	If you have lung problems: - I intend to use my preventer inhaler daily - I intend to carry my reliever inhaler with me
Other intentions (not advised behaviours) ^a	- I will wear a mask as a protection from air pollution - I intend to reduce length or level of my physical exercise indoors

Notes: ^a Measured on 9-point scales, where 1=strongly disagree to 9=strongly agree; ^b From 1 Not at all to 9 all of the time; ^c Possible answers: yes, no, not sure; ^d From 1 Not at all, to 7 more than 150 minutes; ^e Possible answers: Low, Moderate, High, Very High, Not sure, I did not receive any alert; ^f From 1=not at all likely to 9=extremely likely; ^g on a 5-point scale; ^h 1= not clear at all to 9= extremely clear. Demographic data will be collected for all the participants in the first questionnaire.

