6.2 Qualitative data

Qualitative data will be subject to content analysis, with the aim of summarising and systematising the data (39). Respondents' answers will be read repeatedly to familiarise the researcher with the data. Deductive analysis will be used to identify barriers and facilitators to behaviour change in response to receiving air quality alerts. The identified factors will be categorised within the components of the COM-B model (29) to facilitate a comparison with previous literature. Triangulation with a member of the research team will be used to validate the themes developed.

7 Consent

As this research uses online surveys, no written consent will be taken. However, all potential participants will be provided with full details in the participant information sheet (PIS), which clearly states that participation is entirely voluntary, and that completing any surveys online will indicate their consent to participate.

The PIS will be made available to potential participants both when first contacted via the app. They will have all the time they want to consider participation, and to get in touch with the researchers for questions and clarifications.

Participants will be also informed that while they can withdraw from participation at any time, once they have submitted their answers, they will not be able to withdraw their data.

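### Preventer and reliever inhaler items are asked of anyone with lung problems, with no way to say the inhaler is not held, so the planned medication analyses risk attenuation

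*Combined protocol and SAP*

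**What the plan says.** In Section 5.6, Table 4, the medication blocks are introduced by one condition, "If you have lung problems". They cover intentions (baseline and 4 weeks), alert-period adherence, response efficacy, self-efficacy and response costs.

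- **Alert-period items:** "I used my preventer inhaler daily" and "I carried my reliever inhaler with me when going outdoors". The table notes give "Possible answers: yes, no, not sure". A no is followed by a free-text box for reasons.
- **Intention and belief items:** a 1 to 9 agreement scale, with no text box. One response-efficacy item reads "Taking my preventer medications daily is effective in helping me to control my asthma", although it is put to every lung condition.
- **Intervention message (Section 5.5, Table 3, lung-specific and combined columns):** "If you have a preventer inhaler, using it every day will reduce the inflammation that causes asthma".
- **Entry (Section 5.4.2):** participants say whether they have a pre-existing health condition. Inhaler possession is not mentioned.
- **Analysis:** Section 6.1 plans ANCOVAs of all the intention measures, adjusted for baseline, and chi-square tests of self-reported behaviour change in a real episode. It does not name the medication adherence items. On free text, Section 6.2 says "Qualitative data will be subject to content analysis, with the aim of summarising and systematising the data".

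**The concern.** The message is conditional on having a preventer; the items that measure the response to it are not. The plan therefore recognises that some lung participants have no preventer, but does not carry this into the questionnaire. A person who has only a reliever, or whose lung condition is managed without inhalers, has no answer that fits.

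The plan handles the same problem elsewhere. The alert-recall item lets people say they received no alert, and the note to Table 3 explains that messages were tailored so that nobody receives irrelevant ones.

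The inhaler messages are what distinguishes the lung-specific and combined columns of Table 3 from the others, so these items are the direct test of that tailoring. If people who cannot respond to the advice are averaged in, a real effect on medication intentions or use looks smaller than it is, and reported adherence is too low.

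**Working it through.** **Plan's own figure.** There is none for the medication items. The only size in the documents is the minimum of 240 in Section 5.3, set for the main outcome measures. Nothing below depends on how that number was derived.

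**Which items are affected**

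| Items | Answer format | Reasons box | Named in 6.1 |
|---|---|---|---|
| Medication intentions, baseline and 4 weeks | 1 to 9 | No | Yes, within the intention ANCOVAs |
| Alert-period inhaler items | Yes / no / not sure | Yes, after a no | No |
| Medication response efficacy and self-efficacy | 1 to 9 | No | Not stated whether the medication versions are included |
| Medication response costs | 1 to 9 | No | Not stated; these are general beliefs that anyone can answer |

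**Intention items.** Let k be the share of analysed lung participants without the inhaler, similar in both arms on average because of randomisation. Let D be the mean difference among holders. Assume non-holders give the same answers in either arm. The difference over everyone is then

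(1 − k) × D + k × 0 = (1 − k)D.

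If D were 1 point on the nine-point scale, it would appear as 0.8, 0.7 or 0.5 points at k = 20%, 30% or 50%. Adjusting for the baseline item can absorb some of the variation between holders and non-holders, because non-holders answer low both times. It does not restore D.

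**Yes/no items, illustration only.** Assumed inputs, none from the documents: daily use among holders of 60% against 40%; non-holders all answer no and are kept in; k of 20%, 30% or 50%; 30, 50 or 97 lung participants per arm (97 gives 80% power when k = 0). The observed rate in each arm is p(1 − k). Power is for the pooled two-proportion z-test, two-sided 0.05:

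Φ{[d − 1.96√(2p̄(1 − p̄)/n)] / √([p₁(1 − p₁) + p₂(1 − p₂)]/n)}.

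Worked case, k = 20%, n = 50:
- Everyone kept: rates 48% and 32%, d = 0.16. (0.16 − 1.96 × 0.0980)/0.0967 = −0.33, so power is 37%.
- Holders only: n = 50 × 0.8 = 40, d = 0.20. (0.20 − 1.96 × 0.1118)/0.1095 = −0.17, so power is 43%.

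| k | Observed rates | Difference | Power, 30 per arm: all / holders | 50 per arm: all / holders | 97 per arm: all / holders |
|---|---|---|---|---|---|
| 20% | 48% v 32% | 16 points | 24% / 28% | 37% / 43% | 63% / 71% |
| 30% | 42% v 28% | 14 points | 20% / 25% | 31% / 39% | 53% / 65% |
| 50% | 30% v 20% | 10 points | 14% / 19% | 21% / 29% | 36% / 50% |

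Other assumed rates give the same pattern. For 70% against 50% with 93 per arm, power is 59%, 49% and 32% with everyone kept, against 71%, 65% and 50% in holders. In every case the smaller, correct denominator has more power than the larger, mixed one.

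**The case against.** **Scoring.** A reader might infer that people without the inhaler are scored as non-adherent. The documents do not say so. They give no scoring rule, no denominator, no handling of not sure or missing answers, and no statement that items are mandatory. Some non-holders may skip. This stands: dilution follows only if non-holders answer and are kept in.

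**Absence.** Table 4 is a summary, and the wording of the health-status question is not given. The five columns of Table 3 imply that more than a yes/no health question is asked. So possession might be collected without being described. That is possible, but neither the measures nor the analysis section uses it.

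**Text box.** The box after a no could identify some non-holders on the alert-period items. It could, but the plan sends free text to content analysis and provides no recoding. The intention items have no box at all.

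**Response costs.** It is tempting to include these items. They ask whether daily preventer use is unsafe or creates dependence, which anyone can judge, and disagreement is the favourable answer. They do not belong in this point.

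**The calculation.** Section 6.1 does not name the medication adherence items for the chi-square test, so the power table does not describe a stated analysis and cannot stand in for the ANCOVA. Its inputs are all assumed; 50 lung participants per arm would already be 100 of 240, or 42%. At 30 or 50 per arm, power is low even in holders, so the change does not rescue an underpowered comparison. All of this stands. The reduction by the factor (1 − k) does not depend on those rates or numbers.

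**Importance.** The primary questions do not name medication, and three of the five example messages in the lung column concern routes and exercise. This stands and limits the weight of the point.

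**Conclusion.** The point holds as a measurement and denominator gap. The preventer and reliever intention, alert-period, response-efficacy and self-efficacy items go to people to whom they may not apply, and no described step identifies those people.

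If they are kept in, the between-arm difference is multiplied by about (1 − k) and adherence is understated. This assumes that k is similar across arms and that non-holders do not respond to the message. The documents do not give k, so the size is unknown; the 16, 14 and 10 points are illustrations.

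A reader might infer bias towards one arm. Randomisation makes the expected result attenuation and lost power instead. The medication intention ANCOVAs are the most exposed: Section 6.1 covers them, they have no text box, and without possession recorded at baseline the answers cannot be sorted reliably afterwards. The analysis is secondary and confined to the lung subgroup, but the repair is cheap enough to be worth making.

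**What to change.** 1. In the first questionnaire, ask whether the participant has a preventer and whether they have a reliever. The natural place is beside the health-condition question, before the allocated advice is read. Alternatively, add an option such as 'I do not have this inhaler' to the intention, alert-period, response-efficacy and self-efficacy items.
2. In Section 6.1, state that each of these items is analysed only in participants who have that inhaler at baseline, name the analysis of the alert-period medication items, and say how not sure and missing answers are handled.
3. Align the response-efficacy item about asthma with its gate, either by rewording it to refer to the lung condition or by asking it only of people with asthma.
4. Leave the response-cost items as they are.

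The cost is one or two survey questions, a short addition to Section 6.1, and a smaller denominator for a lung-subgroup analysis. If possession is already collected, only the Section 6.1 text and the asthma wording need to change. No advice to participants is altered.
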